Protocol

Safety, Effectiveness, and Mechanism of Fish Oil as Adjunct Treatment for Major Depressive Disorder - a 12-month Randomized, Placebo Controlled Clinical Trial

Unique Protocol ID: MDD201610

Version number: 0001

Date: October 9, 2016

Second Xiangya Hospital of Central South University

Brief Summary

Unique Protocol ID	MDD201610
Official Title	Safety, Effectiveness, and Mechanism of Fish Oil as Adjunct Treatment for Major Depressive Disorder - a 12-month Randomized, Placebo Controlled Clinical Trial
Version number/Date	0001/October 9, 2016
Sponsor	Second Xiangya Hospital of Central South University
Indication	Major Depressive Disorder
Aim	To investigate the role of n-3 polyunsaturated fatty acids in the treatment of depression.
Study Design	Randomized, double-blind, placebo-controlled Clinical Trial
Number of cases	Experimental Group:60, Placebo Group:60
Number of research centers	2
Estimated Primary Completion Date	October, 2019
Study Arms	Placebo Comparator: Placebo (Soybean oil placebo capsules, 8 capsules daily for 24 weeks) Experimental: Fish oil (fish oil capsules, 8 capsules(containing EPA 1440mg, DHA 960mg) daily for 24 weeks)
Outcome Measures	Primary Outcome Measures: HAM-D ₂₄ , HAMA, BDI, SAS Secondary Outcome Measures: CGI-S, CGI-I, SERS, RBANS, STROOP, BMD, MRI
statistical analysis	SPSS

Safety, Effectiveness, and Mechanism of Fish Oil as Adjunct Treatment for Major Depressive Disorder - a 12-month Randomized, Placebo Controlled Clinical Trial

In this proposed study, we will evaluate the effects of fish oil add-on in treatment of major depressive disorder (MDD). Patients are randomly assigned to two groups (n=60): control group (placebo, soybean), fish oil group (fish oil capsules containing about EPA 1440mg, DHA 960mg). The experimental group will be compared to placebo group to evaluate if it may benefit clinical symptoms, cognitive symptoms and metabolic markers in depressive patients. We also plan to investigate the changes in markers of inflammation at the same time. The study will be carried out in the Second Xiangya Hospital of Central South University in China and recruit 120 depressive patients. Only outpatients will be recruited and the enrolled patients will be assessed (baseline). Eligible participants will be between the ages of 18-60. Subjects will be assessed at baseline, week 4, week 8, week 12, week 24 and week 48.

The specific aims are to compare fish oil versus placebo on: 1) clinical symptoms; 2) neurocognitive performance (NP); 3) metabolic markers; 4) makers of inflammation. We hypothesize that: 1) Fish oil add-on therapy is superior to placebo in the treatment of symptoms in patients with MDD, measured by the HAMD and CGI; 2) Fish oil add-on therapy is superior to placebo in the treatment of cognitive symptoms in patients with MDD, measured by the RBANS and STROOP; and 3) Fish oil add-on therapy is superior on alleviating the change of metabolic and inflammation markers induced by antidepressants compared to placebo.

1 Background and significance

Major Depressive Disorder (MDD) is characterized by markedly decreased mood, cognitive capacities and behavior, changes in sleep and appetite, and social functioning deficits. The treatment of depressive symptoms in MDD has made some progress since SSRIs were developed. However, the complete remission in MDD patients remains a major challenge with currently available antidepressant mono-therapies providing only modest benefit. And the pathogenesis of depression has not yet been defined.

Long-chain polyunsaturated fatty acids (LC-PUFAs) are essential fatty acids that primarily found in fish oil and play crucial roles in mechanisms of MDD. Omega-3 polyunsaturated fatty acids (Ω -3 PUFAs),

especially eicosapentaenoic acid (EPA, C20:5n-3) and docosahexaenoic acid (DHA, C22:6n-3) are crucial for the body development. Although studies have shown that reduced N-3 PUFAs were correlated with MDD, and patients with an elevated rate of N-6 PUFAs /N-3 PUFAs or a low level of DHA may be at higher odds for suicide. Trials on whether N-3 PUFAs is effective in the treatment of MDD is still controversial, which might be affected by several factors, such as dose, duration etc.. Now there is no large-scale randomized controlled clinical trial in determining the effects of N-3 PUFAs add-on in treatment of MDD.

The modulate effect of Ω -3PUFAs on the pathology of depression are still unclear. Among many hypotheses, the neuroimmune theory continues to generate substantial interest. Several studies in both humans and animals have provided evidence for a link between the inflammatory process and the depressive disorders. Other possible assumption may be related to its effects on multiple neurotransmitter systems, such us glutamatergic system, dopaminergic system, noradrenergic system and serotonergic system. Moreover, fatty acids-alterations may also alter the feedback of the HPA-axis.

2 Study design

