2.1 Overall Research Design

We will conduct a 48-week randomized, double-blind, placebo-controlled study to investigate the effects of adding fish oil to existing therapy for patients with MDD on: 1) reduce of clinical symptoms (measured by HAMD and CGI) 2) Cognitive improvement (measured by RANSE and STROOP); 3) Safety (UKU, BDI, SAS and clinical lab test) and 4) the biological indicator in blood serum, plasma and lymphocytes of patients between treatment groups and their correlation to clinical symptoms change.

The participators will take fish oil or placebo add-on to existing therapy for 24 weeks and the clinical symptoms, cognition, safety and blood samples will be assessed and collected before and after treatment (baseline, week 4, week 8, week 12, week 24 and week 48). The Evaluation scales used during the follow-up period are as follow:

HAMD (Hamilton depression scale);

HAMA (Hamilton anxiety scale);

CGI (Clinical global impression);

RBANS (Repeatable battery for the assessment of neuropsychological status);

STROOP (Stroop color-word test);
UKU (The UKU side effects rating scale);
CTQ (Childhood trauma questionnaire);
SSRS (Social support rating scale);
SAS (Self-rating anxiety scale);
BDI (Beck depression inventory);
ASEX (Arizona sexual experience scale);
HCL-32 (Hypomania Check List).

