The primary outcome measures will be the clinical symptoms Changes in Hamilton Depression Scale HAMD 6 weeks at week 0, week 4, week 12, week 24 and week 48 among study groups. Secondary outcome measures the Changes in Clinical Global Impression (CGI), Hamilton Anxiety Scale (HAMA), Beck Depression Rating Scale (BDI) and Self-Rating Anxiety Scale (SAS) at week 0, week 4, week 12, week 24 and week 48. And time to relapse for the maintenance phase of the study among study groups.

For hypothesis: Subjects who are randomized to the fish oil will have reduced clinical symptoms and perform better in cognition and improve metabolic markers; inflammation markers than those who are randomized to placebos.

Analyses: After transformation (if necessary to insure the improvement is linear), the difference in the rate of HAMD improvement of fish oil group will be compared with that of the placebo group and the linear mixed effects models will be performed using subjects as the random effect (i.e. the drug-time interaction, with adjustment for baseline values). Secondary analyses will include using GLM to test if treatment arms show effect on CGI, HAMA, BDI, SAS, and other psychological variables. We will also evaluate possible cofounders as well as improvement of neurocognitive domains score and CGI.

4 Key investigator list

Principal Investigator (PI)

[name]. M.D.

Chief Clinical Professor

Mental Health Institute

Second Xiangya Hospital of Central South University

[name]

[contact]

E-mail: [contact], or [contact]

[name]. M.D. (Co-PI)

Department of Pharmacy Xiangya Hospital, Central South University

[name]

[contact]

E-mail: [contact]

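### The Brief Summary names four primary outcomes and Section 3 names HAMD alone; nothing says which list governs, so the primary claim can be settled after the data are seen.

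*Combined protocol and SAP*

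**What the plan says.** The Outcome Measures row of the Brief Summary has "Primary Outcome Measures: HAM-D ₂₄ , HAMA, BDI, SAS", followed by "Secondary Outcome Measures: CGI-S, CGI-I, SERS, RBANS, STROOP, BMD, MRI".

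Section 3 (Overall Approach to Statistical Analysis) has a different hierarchy. Its "primary outcome measures will be the clinical symptoms Changes in Hamilton Depression Scale HAMD 6 weeks", and no other scale is called primary. It continues: "Secondary outcome measures the Changes in Clinical Global Impression (CGI), Hamilton Anxiety Scale (HAMA), Beck Depression Rating Scale (BDI) and Self-Rating Anxiety Scale (SAS". It then adds "time to relapse for the maintenance phase of the study among study groups".

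The analysis paragraph of Section 3 follows the HAMD-only list. A linear mixed model is specified in which "the difference in the rate of HAMD improvement of fish oil group will be compared with that of the placebo group", while "Secondary analyses will include using GLM to test if treatment arms show effect on CGI, HAMA, BDI, SAS".

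Section 2.1 groups measures by aim and places two of the disputed scales under "Safety (UKU, BDI, SAS and clinical lab test". The aims after the Brief Summary and Section 2.1 both pair HAMD with CGI for symptoms and call neither primary.

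Section 3 sets a two-sided 5% level for every test unless stated otherwise. No multiplicity rule appears anywhere.

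**The concern.** HAMA, BDI and SAS are primary in one current section and secondary in another. This is version 0001 with no amendment log, so neither list can be set aside as superseded.

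The primary outcome defines the confirmatory claim. A report that follows the summary could present a result on any of four scales at 5% as a positive primary finding and cite the protocol accurately. A report that follows Section 3 could do so for HAMD only. With both lists in force, the choice can be made after the results are known, and a reader cannot check the claim against the plan. This concerns what the text permits; it is not evidence that anyone has made such a choice.

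**Working it through.** **Text comparison**

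| Measure | Brief Summary | Section 3 | Section 2.1 |
|---|---|---|---|
| HAMD | Primary (24-item) | Primary (no version given) | Symptoms, with CGI |
| HAMA | Primary | Secondary | Listed, no tier |
| BDI, SAS | Primary | Secondary | Safety |
| CGI | Secondary | Secondary | Symptoms, with HAMD |
| RBANS, STROOP | Secondary | Not in the outcome list; cognition mentioned in the hypothesis and analysis text | Cognition |
| SERS, BMD, MRI | Secondary | Not in the list | Not named |
| Time to relapse | Absent | Listed after the secondary scales | Absent |

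HAMD is primary under both lists. What is open is whether HAMA, BDI and SAS are primary too. The Section 3 outcome sentence also contains a stray reference to 6 weeks, although Table 1 has no week-6 visit (baseline and weeks 4, 8, 12, 24 and 48).

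**Size of the consequence**

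From the documents: four scales, two-sided 5% per test (critical value 1.96), 60 patients per arm. Assumed: a common correlation ρ between the four test statistics, since the documents give none. There is no stated error rate or power to reproduce.

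Write Zᵢ = √ρ·U + √(1−ρ)·Eᵢ, with U and the Eᵢ independent standard normal, and integrate over U.

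*(a) Section 3 governs.* There is one HAMD test at 5%, and the other three scales add nothing.

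*(b) Summary governs, all four must be significant.* With all four scales null, the chance that all four are significant in the same direction is 0.6%, 1.9% and 2.6% at ρ = 0.7, 0.9 and 0.95. These are the low case. If three scales have a true standardised difference of 0.5 and one is null, a false all-four claim in favour of fish oil has probability about 2.4% to 2.5% at ρ = 0.5 to 0.9. The error never exceeds 5%.

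*(c) Summary governs, any one scale counts.* At ρ = 0 the two-sided figure is 1 − 0.95⁴ = 0.185 and the figure favouring fish oil is 1 − 0.975⁴ = 0.096. With all four null:

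| ρ | Any false positive, either direction | Any false positive favouring fish oil |
|---|---|---|
| 0 | 18.5% | 9.6% |
| 0.5 | 15.6% | 7.8% |
| 0.7 | 13.0% | 6.5% |
| 0.9 | 9.4% | 4.7% |
| 0.95 | 8.0% | 4.0% |
| one test | 5% | 2.5% |

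**Power under each remedy**

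Assume a standardised difference d = 0.5, no dropout and a normal approximation. The expected test statistic is 0.5 × √(60/2) = 2.74.

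- Single HAMD test at 5%: P(Z > 1.96 − 2.74) ≈ 78%.
- Holm across four and all-four rule, with every scale having d = 0.5:

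| ρ | HAMD under Holm | At least one scale under Holm | All four significant |
|---|---|---|---|
| 0.5 | 69% | 87% | 53% |
| 0.7 | 68% | 81% | 59% |
| 0.9 | 66% | 72% | 68% |

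- Holm when only HAMD has an effect: HAMD power is about 60%, close to the 59.5% from testing it at 0.05/4 = 0.0125.

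Simulated two-sample t-tests give Holm figures about 1 to 2 points lower.

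**The case against.** The strongest reply is that Section 3 settles the matter in substance. HAMD is in both lists, the only mixed model is written for HAMD, and the other scales are explicitly put under secondary analyses. On that reading there is no inflation, and the 8.0% to 18.5% range needs an any-one rule that no section states. This stands as a limit on size: the case rests on the textual conflict, not on those percentages. It does not remove the conflict, because a better supported reading is still not a stated one, and the summary remains quotable as it is.

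Several side points also have some force:

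- Section 2.1 groups measures by aim, so its Safety label does not set an outcome tier.
- SERS may be the UKU side effects rating scale under another abbreviation, though the documents do not confirm it.
- Section 3 touches on cognition outside its outcome list.
- The missing HAMD version in Section 3 is an omission, not a rival version.
- The power figures come from a two-group comparison of means, not from the planned rate-of-improvement model, so they illustrate the trade-off and do not cost the actual test.

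None of these affects the disagreement over which scales are primary.

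**Conclusion.** The concern holds and must be fixed. Two current sections give incompatible primary outcomes, and nothing in the document ranks them. HAMD alone is the better supported reading and carries no inflation from the other scales. The worst reading, four unadjusted alternatives, gives a false-positive chance of 18.5% falling to 8.0% as the correlation rises from 0 to 0.95, and tending to 5% as it nears 1. Requiring all four would keep the error within 5% but cost power. The defect itself is certain from the text; its numerical size depends on an unstated success rule and on assumed correlations.

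**What to change.** Before unblinding:

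1. In the Brief Summary, make HAMD the single primary scale, as in Section 3, and move HAMA, BDI and SAS to secondary.
2. Name one HAMD version in both places, and remove or explain the 6-week reference.
3. Reconcile the two secondary lists (SERS, RBANS, STROOP, BMD, MRI, time to relapse) and the Safety label for BDI and SAS in Section 2.1.
4. Test HAMD at two-sided 5% with one prespecified contrast from the Section 3 mixed model. Section 3 already names the drug-by-time interaction with baseline adjustment; which contrast of it is primary is a separate decision for the sponsor.

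If the sponsor prefers four primaries, the plan must state whether one or all must succeed and, for an any-one rule, apply Holm across the four.

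Reconciling the lists and the scale version is wording only and costs the HAMD test no power. The downside is that a positive HAMA, BDI or SAS result becomes supportive only. Keeping four with Holm would, under the assumptions above, lower HAMD power from about 78% to between 66% and 69% if all scales share the effect, and to about 60% if only HAMD responds. In return, power for at least one scale would be 72% to 87% if all share it.

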2.1 Overall Research Design

We will conduct a 48-week randomized, double-blind, placebo-controlled study to investigate the effects of adding fish oil to existing therapy for patients with MDD on: 1) reduce of clinical symptoms (measured by HAMD and CGI) 2) Cognitive improvement (measured by RANSE and STROOP); 3) Safety (UKU, BDI, SAS and clinical lab test) and 4) the biological indicator in blood serum, plasma and lymphocytes of patients between treatment groups and their correlation to clinical symptoms change.

The participators will take fish oil or placebo add-on to existing therapy for 24 weeks and the clinical symptoms, cognition, safety and blood samples will be assessed and collected before and after treatment (baseline, week 4, week 8, week 12, week 24 and week 48). The Evaluation scales used during the follow-up period are as follow:

HAMD (Hamilton depression scale);

HAMA (Hamilton anxiety scale);

CGI (Clinical global impression);

RBANS (Repeatable battery for the assessment of neuropsychological status);

STROOP (Stroop color-word test);
UKU (The UKU side effects rating scale);
CTQ (Childhood trauma questionnaire);
SSRS (Social support rating scale);
SAS (Self-rating anxiety scale);
BDI (Beck depression inventory);
ASEX (Arizona sexual experience scale);
HCL-32 (Hypomania Check List).

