2.4 Assessment

Following consent, patients met enrollment criteria to be in the study will be undergone assessments including:

- ① Demographic information, medical and psychiatric history and family history of mental illnesses at baseline;
- ②Labs: CBC, metabolic panel, liver panel and lipid panel (extra sample will be saved for biomarkers);

- ③Clinical symptom will be assessed by HAMD;
- ④Cognitive assessment by RBANS and STROOP;
- ⑤Side effect rated on UKU and Lab tests.

Almost all clinical assessments will be done at baseline, week 4, week 8, week 12, week 24 and week 48, except some items being done at baseline only (See table 1 for details).

For the lab work, in addition to routine clinical safety lab, some extra blood sample will be collected and stored for future epigenetic and bio-inflammatory biomarkers assay.

Table 1: Schedule of Clinical, Neurocognitive Assessment and Lab testing for Evaluation of fish oil add-on therapy in MDD

	Baseline	W04	W08	W12	W24	W 48
Inform consent	*					
Inclusion/exclusion screen	*					
Demographic & medical, mental illness history	*					
Physical exam	*	*	*	*	*	*
Lab test and blood sample stored	*	*		*	*	*
Randomization	*					
Study medication dispense	*	*	*	*		
HAMD, HAMA, CGI, BDI, SAS, RBANS, STROOP, ASEX, Somatic Self-rating Scale	*	*	*	*	*	*
CTQ, SSRS	*					
UKU		*	*	*	*	*
BMD	*				*	*
MRI	*				*	*

3 Overall Approach to Statistical Analysis

Data will be examined for obvious outliers, distribution irregularities, and range errors and processed accordingly. Prior to analyses, the validity of assumptions (e.g., about distributions) will be confirmed. Transformations will be made or a nonparametric procedure may be utilized as needed. Means, standard deviations, ranges or interquartile ranges, and rates of primary outcomes will be reported. Baseline demographics and characteristics will be compared among study groups using F-tests or chi-square tests

or nonparametric equivalents as needed. Baseline variables with significant group differences will be treated as potential confounder variables and will be statistically adjusted for in analyses. Unless stated otherwise, two-sided testing and a 5% level of significance are planned for all statistical tests.

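### Table 1 omits the baseline UKU that sections 2.1 and 2.4 imply, so change from baseline and new-onset items on the only named side-effect scale cannot be derived for individual patients.

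*Combined protocol and SAP*

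**What the plan says.** Section 2.1 defines the safety domain as "Safety (UKU, BDI, SAS and clinical lab test". It then gives the timing: "clinical symptoms, cognition, safety and blood samples will be assessed and collected before and after treatment (baseline, week 4, week 8", followed by weeks 12, 24 and 48. Read together, these place the UKU at baseline.

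Section 2.4 lists UKU and laboratory tests, as the means of rating side effects, among the assessments made after consent. It says nearly all clinical assessments occur at all six time points, "except some items being done at baseline only (See table 1 for details". That exception covers items done only at baseline. It does not describe an item left out at baseline.

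Table 1 has the columns "Baseline W04 W08 W12 W24 W 48". The UKU row is empty under baseline and marked at the other five visits. The row "HAMD, HAMA, CGI, BDI, SAS, RBANS, STROOP, ASEX, Somatic Self-rating Scale" is marked at all six. The row "Lab test and blood sample stored" is marked at baseline and weeks 4, 12, 24 and 48, but not at week 8.

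On background treatment, section 2.1 states: "The participators will take fish oil or placebo add-on to existing therapy for 24 weeks".

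**The concern.** Side-effect scales record complaints, and many complaints in this population will predate the capsules. Patients need a HAMD total of at least 21 to enter, section 1 itself names sleep and appetite changes as features of the disorder, and patients are already receiving other treatment. A UKU item scored at week 4 could be a symptom of depression, an effect of the existing therapy, or an effect of the capsules. Without a UKU score from before the first capsule, that item cannot be classed as new, worse or unchanged on its own scale.

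Two further consequences follow. First, section 3 adjusts the HAMD model for baseline values and promises adjustment for baseline variables that differ between groups; neither is possible for the UKU as scheduled. Second, both arms take eight 1 g oil capsules a day. A complaint caused equally by both oils would not appear in the comparison between arms. A within-arm rise from baseline could point to it, though that change is not placebo-controlled, and on the UKU it cannot be seen at all.

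The loss is permanent for each patient once capsules have started. Safety is also the first word of the trial's title.

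**Working it through.** **Step 1: schedule check.** The plan states no figure to reproduce here, so the check sets section 2.1 against Table 1 for each of the four safety components.

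| Component (section 2.1) | Baseline | W04 | W08 | W12 | W24 | W48 |
|---|---|---|---|---|---|---|
| UKU | no | yes | yes | yes | yes | yes |
| BDI | yes | yes | yes | yes | yes | yes |
| SAS | yes | yes | yes | yes | yes | yes |
| Laboratory tests | yes | yes | no | yes | yes | yes |

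Section 2.1 implies yes in every cell. Two cells disagree: UKU at baseline and laboratory tests at week 8. UKU is the only component without a baseline.

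**Step 2: precision of a UKU total (illustration).** The documents give no correlation between baseline and follow-up UKU. Assume r = 0.4 to 0.6. Adjusting for baseline multiplies the variance of the arm difference by 1 − r², and the equivalent sample-size factor is 1/(1 − r²).

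- r = 0.4: 1 − 0.16 = 0.84, a 16% cut; 1/0.84 = 1.19
- r = 0.5: 1 − 0.25 = 0.75, a 25% cut; 1/0.75 = 1.33
- r = 0.6: 1 − 0.36 = 0.64, a 36% cut; 1/0.64 = 1.56

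If other baseline scales already explained 9% of the follow-up variance (assumption), and the total explained with UKU stayed at 16% to 36%, the further gain would be smaller. At the low end 0.84/0.91 = 0.92, an 8% cut; at the high end 0.64/0.91 = 0.70, a 30% cut.

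**Step 3: attribution of a single complaint (illustration).** Let b be the proportion of patients with the complaint before the capsules. Assume it persists in all of them, and that new complaints arise in 20% of the remaining fish oil patients and 5% of the remaining placebo patients. The observed proportion is b + (1 − b)p. The share of fish oil complaints that were already present is b divided by that proportion.

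| b | Fish oil observed | Placebo observed | Difference | Fish oil share already present |
|---|---|---|---|---|
| 0.10 | 0.10 + 0.90 × 0.20 = 0.280 | 0.10 + 0.90 × 0.05 = 0.145 | 0.135 | 0.10/0.280 = 36% |
| 0.30 | 0.30 + 0.70 × 0.20 = 0.440 | 0.30 + 0.70 × 0.05 = 0.335 | 0.105 | 0.30/0.440 = 68% |
| 0.50 | 0.50 + 0.50 × 0.20 = 0.600 | 0.50 + 0.50 × 0.05 = 0.525 | 0.075 | 0.50/0.600 = 83% |

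All of these rates are assumed. Full persistence is the extreme case; complaints that resolve as depression improves would lower the shares. The direction does not depend on the exact rates: persisting complaints dilute the visible difference, and follow-up UKU scores alone cannot separate them from new ones.

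**The case against.** The strongest reply is that the plan is not blind to prior complaints. Table 1 collects ASEX, the Somatic Self-rating Scale, HAMD, HAMA, BDI, SAS, physical examination and laboratory tests at baseline and again later, with medical history at baseline. Sexual problems, for example, have their own scale at all six visits. This stands. A reader might infer that complaints present before treatment cannot be told from new ones at all, or that the trial cannot report treatment-emergent effects. The documents do not support either inference: emergent laboratory, sexual and somatic changes can still be reported. These measures are different instruments, however, and do not supply UKU item-level change or onset.

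A second reply is that three of the four safety components do have a baseline, so the visit list in section 2.1 may be read as a summary of the domain, and section 2.4 says only that nearly all assessments follow the full schedule. That softens the conflict but does not remove it. The exception in section 2.4 runs the other way, and nothing explains the empty cell. The sponsor may have reasoned that side effects cannot precede the study capsules, but patients are already on other therapy.

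Third, the blinded placebo arm is itself a reference, so randomisation keeps the comparison of post-baseline UKU scores unbiased. This also stands. It would be wrong to infer that the safety comparison is biased.

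Finally, section 3 specifies no UKU analysis, and UKU is not in the outcome list of the Brief Summary. The percentages therefore describe a comparison the plan has not yet defined, under a correlation it does not give. They show scale only.

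**Conclusion.** The point holds in a limited form. The inconsistency is certain: sections 2.1 and 2.4 imply a baseline UKU and Table 1 omits it. It follows without any assumption that UKU change from baseline and new-onset UKU items cannot be derived for individual patients.

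The between-arm comparison remains valid but is less precise than it could be. How much less is not known from the documents: 16% to 36% of the variance of a UKU total under an assumed correlation of 0.4 to 0.6, and less if other baseline scales are adjusted for. The loss concerns the UKU alone and does not touch the primary HAMD analysis. The change should be made, because the omission cannot be repaired after treatment starts and costs little to avoid.

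**What to change.** Mark UKU at baseline in Table 1, rated at the existing baseline visit before the first capsules, so that the table agrees with sections 2.1 and 2.4. In section 3, state that the baseline value is the reference: a covariate when UKU totals are compared between arms, and the level from which an item must worsen to count as emergent. These two uses are analysis choices that the added rating makes possible; the schedule correction is needed in either case.

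The cost is one more rating per patient, 60 + 60 = 120 in all, at a visit that already takes place. No extra visit is needed.

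In the same edit, reconcile the week 8 blood sample, which section 2.1 lists and the laboratory row of Table 1 leaves unmarked.
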